--	---

Statistical Methods
	
Safety Endpoints:
 
 • Incidence of adverse events, including serious adverse events (SAEs) and clinically significant laboratory abnormalities. • Overall tumor response to treatment using RECIST or site preference criteria. 
Efficacy Endpoints:
 
 • Duration (in days) of severe oral mucositis (SOM, WHO grades 3 or 4) • Time (in days) to onset of SOM • Incidence of SOM • Incidence and duration of ulcerative mucositis (WHO grades 2, 3, 4) • Patient-reported mucositis pain as measured by question 2 of the Oral Mucositis Daily Questionnaire 
Design:
 
This is a randomized, open-label, parallel group, Phase 2 study to assess the safety and radioprotective potential of RRx-001 in patients undergoing chemoradiation therapy for locally advanced head and neck cancer.
 
A total of approximately 40 patients will participate in this study. All patients will receive standard chemoradiation therapy consisting of cisplatin either every three weeks (100 mg/m² for 3 doses) or weekly (40 mg/m² for 7 doses) + radiotherapy (IMRT) administered daily (except weekends) for 7 weeks. In conjunction with this “standard of care” (SOC), patients will be randomly assigned to receive one of 3 regimens of RRx-001 or a control (no treatment).
 
Sample Size:
 
A sample size of approximately 40 patients (~10 per group) is considered adequate for this proof-of-concept (POC) study to explore the radioprotective potential of RRx-001 and identify a safe regimen for further development.
 
Statistical Methods:
 
Efficacy and safety data will be summarized using descriptive statistics, including the mean, standard deviations, median, minimum and maximum for continuous endpoints and frequency tables for categorical data.
 
Efficacy Analysis:
 
Hypothesis testing of efficacy endpoints will be performed for exploratory purposes only. For continuous efficacy endpoints, non-parametric methods will be used to compare each RRx-001 group to the untreated control group (Wilcoxon rank-sum tests). Fisher’s exact test will be used to evaluate treatment differences for binary outcomes. Two-sided 95% confidence intervals will be calculated for proportions using the Clopper-Pearson method.
 
Safety Analysis:
 
Safety data, including adverse events (AEs), serious adverse events (SAEs), ECOG performance status, clinical laboratory tests, vital signs and physical examination results will be listed and summarized descriptively by treatment group. Adverse events will be coded by system organ class (SOC) and preferred term using MedDRA (Version 18.1), and severity will be based on NCI CTCAE Grade criterion (Version 5.0).
 
Descriptive statistics (sample size, mean, median, standard deviation, quartiles and range) and graphical methods (longitudinal plots) will be used to present change from pre-treatment values in laboratory parameters during the treatment period. The incidence of febrile neutropenia, bacterial infections, grade 3 or 4 cervicofacial dermatitis, and other toxicities of clinical interest (xerostomia, trismus, fatigue, weight loss, radiation dermatitis, and dysgeusia) will be tabulated by treatment arm.

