13.2 Efficacy Analysis

Statistical methods for the calculation and analysis of efficacy endpoints are provided below. Limited hypothesis-testing will be performed, as this is a small POC study. All statistical analyses are exploratory.

Duration of Severe Oral Mucositis (SOM): The duration of SOM (WHO grade 3 or 4) will be calculated as the number of days from the onset of SOM (first time a WHO grade 3 or 4 is observed) to the day when severe OM has resolved (first time WHO grade 2 or less is observed after last WHO grade 3 or 4). Durations of 0 will be assigned to patients who do not experience severe OM. Any patient who dies or withdraws prior to resolution of severe OM will be assumed to have severe OM for the remainder of the observation period. All available OM assessments will be used to derive efficacy endpoints, including WHO grades recorded during the treatment and follow-up period in order to capture resolution of OM.

The duration of SOM will be compared for each of the 3 RRx-001 regimens versus the untreated control group using the Wilcoxon rank-sum test. This rank-based test does not depend on normality assumptions for these small sample sizes. All patients randomized (the intent-to-treat population) will be used for this analysis.

Time to onset of SOM: The number of days from the start of chemotherapy until the date of first OM assessment grade 3 or 4 will be listed and summarized descriptively for each treatment group.

Incidence of SOM: The incidence of SOM (WHO grade 3 or 4) will be calculated as the number of patients with at least one OM WHO grade 3 or 4, divided by the number patients in the treatment group. Patients with no OM assessments will be assumed to have severe scores. Patients who die or withdraw without experiencing OM grade 3 or 4 will also be assumed to have severe scores. The incidence of SOM will be compared between each RRx-001 group and the control arm using Fisher's Exact test. Clopper-Pearson two-sided 95% confidence limits will be calculated for the proportion of patients with SOM in each treatment arm.

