Pre-study abnormalities and reported abnormalities at the end of study will be tabulated by body system. Changes in physical examinations will be described in the text of the final study report. Tumor response assessments at each follow-up visit will be tabulated by treatment group.

Prior and concomitant medications will be tabulated for each treatment group; details regarding dose regimens and start/stop dates will be presented in by-patient data listings.

Progression Free Survival (PFS) defined from the time of registration to the time of the first radiographic documentation of objective progression (per RECIST v1.1) or the date of death, whichever is earlier, will be evaluated using Kaplan-Meier methods. Subjects still alive without progressive disease at the time of analysis will be censored on the date of the last objective progression-free observation prior to the start of subsequent anti-cancer therapy.

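### Time to onset of severe oral mucositis is defined only for patients who develop it, so its summary can hide a preventive effect

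*Combined protocol and SAP*

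**What the plan says.** The Study Summary (Section 2) lists "Time (in days) to onset of SOM" second among the efficacy endpoints. Section 13.2 sets the origin with the words "The number of days from the start of chemotherapy"; the count then runs, in the plan's terms, "until the date of first OM assessment grade 3 or 4 will be listed and summarized descriptively for each treatment group". It gives no value, censoring rule or time-to-event method for a patient without such an assessment. The synopsis says efficacy data will be summarized by descriptive statistics, "including the mean, standard deviations, median, minimum and maximum for continuous endpoints".

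Neighbouring endpoints do have such rules:

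- **Duration of SOM (Section 13.2):** "Durations of 0 will be assigned to patients who do not experience severe OM", and all randomized patients are analysed.
- **Incidence of SOM (Section 13.2):** patients with no mucositis assessment count as severe, and "Patients who die or withdraw without experiencing OM grade 3 or 4 will also be assumed to have severe scores".
- **Progression-free survival (Section 13.3):** it "will be evaluated using Kaplan-Meier methods", with a censoring rule.

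On testing, the synopsis says: "For continuous efficacy endpoints, non-parametric methods will be used to compare each RRx-001 group to the untreated control group". It names the Wilcoxon rank-sum test and makes no exception for onset. Section 13.2 announces limited testing, names tests for SOM duration and incidence and for ulcerative mucositis, and names none for onset.

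**The concern.** Onset is a time-to-event quantity handled as an ordinary measurement. A patient who never has SOM has the best possible outcome, yet adds nothing to the mean, SD, median or range. A patient who withdraws without SOM counts as severe for incidence but has no onset date, so the two endpoints rest on different sets of cases.

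Comparing arms among cases compares groups formed after randomization by the outcome itself. Section 13.1 expects efficacy trends to inform later designs. An onset table showing no difference could be read as no effect on onset when it only reflects who was included.

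**Working it through.** **The plan's own figure.** None is given for onset. The one design calculation (Section 13.1) concerns SOM duration: 24 v 6 days, SD 13, 10 per group, two-sided 5% t-test. The noncentrality is 18 / (13 × √(2/10)) = 3.10 on 18 df, giving 83.3% power, against the stated approximate 80%. It does not bear on onset.

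**General result, free of assumed rates.** Let f(t) be the probability that a control patient has first SOM on day t, F(t) its running sum, and π = Σ f(t) the incidence. The mean onset among cases is Σ t·f(t) / π. If the drug prevents a fraction q of cases whatever their onset time, f(t) becomes (1 − q)·f(t) and π becomes (1 − q)·π. The factor cancels, so the whole onset distribution among cases is unchanged for any q below 1. The SOM-free proportion at day t rises by q·F(t).

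**Illustration (all hazards assumed).** Control daily hazard is 0.02 on days 14–27 and 0.04 on days 28–62, with observation ending at day 62.

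- Control incidence: 1 − 0.98^14 × 0.96^35 = 82%.
- Control SOM-free at day 42: 0.98^14 × 0.96^15 = 40.9%.
- With q = 0.5, SOM-free at day 42: 1 − 0.5 × (1 − 0.409) = 70.4%.

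| Scenario | Incidence | Cases-only mean / median (days) | SOM-free at end of weeks 3, 4, 5, 6 (%) |
|---|---|---|---|
| Control | 82% | 34.7 / 33 | 85, 72, 54, 41 |
| Half of cases prevented | 41% | 34.7 / 33 | 93, 86, 77, 70 |
| Hazard halved throughout | 57% | 37.8 / 37 | 92, 85, 74, 64 |
| 7-day delay | 76% | 39.8 / 39 | 98, 85, 72, 54 |
| Hazard cut 70% from day 28 only | 51% | 32.3 / 28 | 85, 74, 68, 63 |

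The effect is hidden in row 2 and points the right way in row 3. In row 4 the mean gains 39.8 − 34.7 = 5.1 days instead of 7, because some onsets move past the assumed day-62 cut-off. Row 5 points the wrong way.

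**If onset were tested.** Simulated trials of 10 v 10, two-sided 5%, share significant in the drug's favour (Fisher by exact enumeration):

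| Scenario | Wilcoxon, cases only | Wilcoxon, all patients, never-SOM ranked last | Planned Fisher test on incidence |
|---|---|---|---|
| Half prevented | 2% | 37% | 27% |
| Hazard halved | 6% | 22% | 9% |
| Late cut | 1% | 18% | 15% |
| 7-day delay | 11% | 11% | 1% |

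**A second onset model** gives the same picture. Onset in cases is normal with mean 28 and SD 8 days in both arms, and incidence is 90% in control v 50% to 20% on drug. Cases-only medians are 28 v 28 days. A cases-only Wilcoxon is significant in 2–4% of trials, against 32–85% with non-cases ranked last.

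**The case against.** - **Section 13.2 never says cases only.** A Kaplan-Meier median is also a descriptive summary, so the text could be read as silent. This stands as a point of wording: the restriction is inferred from the definition and the missing rule. But the synopsis names the mean, SD, median and range, and these cannot be computed for a patient with no onset date.
- **A reader might infer that the plan calls for a cases-only Wilcoxon test.** The documents do not support that. Section 13.2 is the more specific text, limits testing, and assigns onset no test, so the natural reading is that onset is not tested. The synopsis merely omits the exception.
- **A reader might infer that the trial would miss prevention, or report it backwards.** Neither follows. Duration with zeros and incidence include every patient; in the second model Fisher's test on incidence reaches 29–84%, close to the all-patient Wilcoxon. Reversal needs mainly late cases to be prevented, which the documents do not predict.
- **The hazards are invented.** This stands. Day 62 is also an assumption, and the shortfall for a delay comes from it. For a pure delay, the all-patient Wilcoxon test gains nothing (11% v 11%). The cancellation under pure prevention does not depend on the rates.
- **Dating withdrawals as events, and choosing a horizon, is debatable.** This stands too, and is why the fix asks for a pre-stated choice and a sensitivity analysis.

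**Conclusion.** The point holds as a gap worth closing before analysis. As defined, onset can be summarized only among SOM cases. If RRx-001 prevents SOM and leaves onset in the remaining cases unchanged, that summary shows no difference at any level of prevention. For other patterns, the size and direction of distortion depend on rates the documents do not give, so the figures above are illustrations.

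The consequence is limited. All analyses are exploratory, no decision rule rests on onset, and incidence and duration will normally reveal prevention. The mismatch between the synopsis and Section 13.2 on testing is minor and needs one clarifying sentence.

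**What to change.** 1. In Section 13.2, summarize time to first SOM by Kaplan-Meier for all randomized patients from the start of chemotherapy. For each arm show the curve, the median if reached, and the SOM-free proportion at fixed radiotherapy weeks, for example 3 to 6.
2. Carry patients who complete mucositis follow-up without SOM as event-free to one pre-stated horizon. Footnote 17 to the Schedule of Assessments (28-day visit) gives 7 + 4 = 11 weeks; Section 6.1 (up to 6 weeks after radiotherapy) gives 7 + 6 = 13 weeks. Do not censor at the last mucositis assessment: under Section 11.1 weekly assessment stops at grade 0 or 1, so that date depends on outcome.
3. Pre-state one handling of death, withdrawal, no mucositis assessment and no start of chemotherapy: either events, matching the incidence rule, or censored. Report the other as a sensitivity analysis.
4. Align the synopsis with Section 13.2: either onset is not tested, or the test uses all randomized patients (log-rank, or Wilcoxon with never-SOM ranked last) and not cases only.
5. Label any days-to-onset summary among cases as cases only, with n.

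The cost is wording and a little analysis of data already collected. With about 10 per arm the curves are imprecise and the median may not be reached. The horizon assumes no new SOM after assessments stop. The incidence rule imputes status, not a date, so event dates are a choice, and each such patient moves a 10-patient curve by about 10 percentage points.

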17. A 28 Day Safety Visit will occur 4 weeks (28 days) post last dose of radiation treatment (+5 day window). If the patient has an OM grade ≥ 2 , patient will continue with the Mucositis Observation Follow-up weekly visits until an OM grade of ≤ 1 is achieved. If the patient finished Combination Treatment with an OM grade ≤ 1 , the patient will return to clinic 28 days post IMRT (+ 5 days) for this 28 Day Safety Visit. Once the patient is assigned an OM grade ≤ 1 and has completed the 28 Day Safety Visit, the patient will proceed into Long Term Follow Up.
18. Long-Term Follow-Up may be performed via chart review. All procedures performed during the follow-up period should be recorded as Concomitant Procedures. Patients should continue to be followed monthly if experiencing an adverse event related to the investigational agent of RRx-001 until resolution, or event is assessed as a grade ≤ 2 .

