	
6. Human papilloma virus (HPV) status in tumor has been documented using tumor immunohistochemistry for HPV-p16 or other accepted test for patients with cancers of the oropharynx, base of tongue, or unknown primary.
 
7. Age 18 years or older
 
8. Patient must consent to the access, review and analysis of previous medical and cancer history, including imaging data by the sponsor or a third party nominated by the sponsor.
 
9. Ability to understand and sign a written informed consent document.
 
10. Women of child-bearing potential and men with partners of child-bearing potential must agree to use adequate contraception (hormonal or barrier method of birth control; abstinence) prior to study entry, for the duration of study participation, and for 90 days following completion of therapy.
 
Note: A woman of child-bearing potential is any female (regardless of sexual orientation, having undergone a tubal ligation, or remaining celibate by choice) who meets the following criteria:
 
 • Has not undergone a hysterectomy or bilateral oophorectomy; or • Has not been postmenopausal for at least 12 consecutive months 
11. Adequate visual access to permit examination of the following oral cavity sites: lips, buccal mucosa, floor of mouth, ventral and lateral tongue and soft palate.
 
Exclusion Criteria
 
 1. Prior radiation to the head and neck 2. Prior induction chemotherapy 3. Tumor of the lips, nasopharynx, hypopharynx, larynx, or salivary glands 4. Patients with simultaneous primaries 5. Stage IV, M1 (distant metastasis) 6. Malignant tumors other than HNC within the last 5 years, unless treated definitively and with low risk of recurrence in the judgment of the treating investigator 7. Presence of oral mucositis (WHO Score \geq Grade 1) or other oral mucosal ulceration at study entry 8. Grade 3 or 4 dysphagia or odynophagia (National Cancer Institute Common Toxicity Criteria, version 5.0) or inability to eat a normal diet 9. Requirement at baseline for parenteral or gastrointestinal tube-delivered nutrition for any reason. Prophylactic placement is allowed. 10. Known history of HIV or active hepatitis B/C (patients who have been vaccinated for hepatitis B and do not have a history of infection are eligible) 11. Any significant medical diseases or conditions, as assessed by the investigators and sponsor that would substantially increase the medical risks of participating in this study (i.e., uncontrolled diabetes, NYHA II-IV congestive heart failure, myocardial infarction within 6 months of study, severe chronic pulmonary disease or active uncontrolled infection, uncontrolled or clinically relevant pulmonary edema). 12. Pregnant or nursing 13. Untreated active oral or dental infection 14. Known allergies or intolerance to cisplatin and similar platinum-containing compounds 15. Evidence of immediate life-threatening disease or a life expectancy of less than 3 months 16. Receipt of unapproved or off-label medication within 30 days prior to start of study treatment, including use of an investigational agent 17. Sjogren syndrome

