11 EFFICACY ASSESSMENTS

11.1 Oral Mucositis (OM) Assessments

Mucositis assessments will be completed at the screening visit, day 1 of pretreatment prior to administration of RRx-001, twice weekly (no less than 48 hours apart) within each 5-day radiation week during the combination treatment phase, at the end of the combination treatment phase (last day of radiation) and the same day each week (± 1 day) during the Mucositis Observation Follow-up until resolution of ulcerative mucositis occurs (WHO grade 0 or 1).

Oral mucositis will be assessed by a trained evaluator using a standard oral mucositis assessment instrument. If a patient withdraws prior to the end of the combination treatment phase, an oral assessment must be completed on the day of withdrawal, and it is suggested that patients be assessed weekly until resolution of ulcerative mucositis occurs (WHO grade 0 or 1). Patients will be instructed not to discuss their treatment regimens with the assessor. Additionally, the assessor will be provided training to assure uniform interactions with patients to limit bias in the assessment.

Specific training and instructions are required for all individuals who perform mucositis assessments. Such training will be provided by the sponsor or its designee. Site study staff

designated as oral evaluators must be licensed professionals and properly delegated such tasks (on DOA log). Oral evaluators will conduct all assessments using a standardized and consistent method. To reduce inter-observer variability, as few oral evaluators as possible should be involved in the assessments of an individual patient. Ideally, the same assessor will evaluate a single patient throughout the combination treatment and mucositis observation follow-up. All efforts to maintain uniformity should be used.

The study's efficacy endpoints will be based on WHO mucositis criteria. Since patients' ability to eat is a component of the WHO scale, standardization of the assessment of food intake and, particularly, the definition of solids, liquids and "nothing by mouth" is critical.

- A normal solid diet is defined as firm, shaped food that does not flow or conform to the shape of its container and requires chewing. Examples include rice, meat including fish, poultry, bread, rolls, toast, salad, cereal.

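### The no-assessment rule for SOM incidence in Section 13.2 is not tied to radiation, so it catches almost nobody, and an on-study patient unscored during radiation can be counted as SOM-free

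*Combined protocol and SAP*

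**What the plan says.** **Incidence (Section 13.2).** SOM incidence is the "number of patients with at least one OM WHO grade 3 or 4, divided by the number patients in the treatment group". Two rules cover missing data. The first is "Patients with no OM assessments will be assumed to have severe scores". The second is "Patients who die or withdraw without experiencing OM grade 3 or 4 will also be assumed to have severe scores".

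**Duration (Section 13.2).** "Durations of 0 will be assigned to patients who do not experience severe OM". The only imputation, which carries SOM forward to the end of observation, is: "Any patient who dies or withdraws prior to resolution of severe OM will be assumed to have severe OM for the remainder". Every randomised patient enters the Wilcoxon comparison, and every available score is used, follow-up scores included. Ulcerative OM is handled in the same way.

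**When scores are taken.** Section 11.1 states: "Mucositis assessments will be completed at the screening visit, day 1 of pretreatment prior to administration of RRx-001". It then requires scoring twice weekly during radiation, on the last radiation day, and weekly afterwards until grade 0 or 1. Footnote 6 of Section 1.2 adds a Day 15 score before chemoradiation begins. Exclusion criterion 7 rules out WHO grade 1 or higher "or other oral mucosal ulceration at study entry", so the mouth has to be examined before entry.

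**Leaving weekly scoring.** Footnote 17 of Section 1.2 moves a patient to long-term follow-up only after a grade of 1 or less and the 28-day visit. Footnote 18 adds: "Long-Term Follow-Up may be performed via chart review".

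**The concern.** The first incidence rule is evidently meant to be conservative: a patient whose mucositis was never observed should not count as a success. As worded, a single score taken before any radiation is enough to escape it, and such a score carries no information about radiation-induced SOM. A patient who remains on study but goes unscored when SOM would appear is then absent from the numerator and present in the denominator. That is the best possible outcome, the reverse of the rule's purpose.

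The bias favours whichever arm holds the unscored patients. The trial is open-label with about 10 patients per arm, and Section 13.1 says its efficacy trends will inform later designs. How such patients are coded should therefore be settled before the data are seen. At present two analysts could code the same patient differently.

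**Working it through.** **1. Patient types set against the text of Section 13.2**

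| Patient | Incidence | Duration |
|---|---|---|
| No OM score at all, screening included | Severe (first rule) | Not stated |
| Dies or withdraws, no grade 3–4 seen | Severe (second rule) | No onset date, so no clear non-zero value |
| On study; pre-radiation scores only, or scoring stops during radiation; no grade 3–4 then or in follow-up | Neither rule applies; SOM-free by the formula | Most naturally 0 |
| On study; unscored during radiation; grade 3–4 found in follow-up | SOM case | Above 0, but from a late onset |
| On study; last score grade 3–4, none later | SOM case | Undefined: no resolution date, no imputation |
| Dies or withdraws with SOM unresolved | SOM case | Runs to the end of the observation period |

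The third and fifth rows are the gap. The second row shows that incidence and duration can disagree even for a patient the plan does cover.

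**2. The plan's own figure (Section 13.1)**

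Inputs: 10 per group, 24 v 6 days (difference 18), SD 13, two-sided 5%, t-test.

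- Noncentrality = 18 / (13 × √(2/10)) = 18 / 5.81 = 3.10 on 18 degrees of freedom.
- Power is 83.3% at n = 10 and 78.7% at n = 9.

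Ten is the smallest group size reaching 80%, so the figure reproduces. The point does not depend on it; only the 18-day effect is used below.

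**3. Effect on incidence**

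One patient in an arm of 10 moves incidence by 1/10 = 10 percentage points. The documents give no rate of missing scores, so the counts below are assumed. With equal arms, two-sided Fisher p is twice the upper hypergeometric tail.

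- 9/10 v 3/10: 2 × (1200 + 45) / 125,970 = 0.020
- 9/10 v 4/10: 2 × (2100 + 120) / 77,520 = 0.057
- 8/10 v 2/10: 2 × (2025 + 100 + 1) / 184,756 = 0.023
- 8/10 v 3/10: 2 × (5400 + 450 + 10) / 167,960 = 0.070
- 8/10 v 4/10: 2 × (9450 + 1200 + 45) / 125,970 = 0.170

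Recoding one unscored RRx-001 patient as severe moves the first line to the second, or the third to the fourth. Recoding two moves the third to the fifth; that arm's Clopper-Pearson interval then goes from 2.5–55.6% to 12.2–73.8%.

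Not every case crosses 0.05. Against 9/10, going from 2/10 to 3/10 moves p only from 0.005 to 0.020.

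**4. Effect on duration**

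Suppose the unscored patient truly had 24 days, the control mean used for planning. Entering 0 lowers the arm mean by 24/10 = 2.4 days, or 2.4/18 = 13% of the planned effect. Two such patients lower it by 4.8 days, or 27%.

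The Wilcoxon test is less sensitive. In 6,000 simulated trials per setting with no true effect (normal, mean 24, SD 13, floored at 0), zeroing 0, 1, 2 or 3 patients in one arm only gave two-sided rejection rates of 3.8%, 3.9%, 6.6% and 12.9%. One zeroed patient barely matters there; three in one arm do.

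**The case against.** **The sentence may mean scores that inform the endpoint.** It sits among rules for on-treatment SOM, so a reader could supply that limit. The text does not, and the neighbouring statement that all available assessments are used gives no help. This supports clarifying the sentence. A reader might also go further and infer that the rule describes a group that cannot exist. That is too strong: a screening score can be missed, and the rule is close to empty only when the protocol is followed.

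**Zero days is not written for unscored patients.** That stands. Zero goes to patients who do not experience SOM, and an unscored patient has not been shown to be one. Zero is the most natural coding because no other value is offered.

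**The lapse has to be long and off-protocol.** Patients attend for daily fractions, are scored twice weekly, and are then scored weekly. Footnote 17 keeps them in weekly scoring until grade 1 or less, so chart review is not an early exit. Section 3.1 puts healing at 2–4 weeks after radiation, so SOM may still be caught in follow-up and make the patient a case. This limits the number affected. It does not say how to code those who remain.

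**Differential loss by arm is not shown.** A reader might infer that patients too ill to attend go unscored, or that Arms 1–3 lose patients in the two-week lead-in. The documents give no support for the first, and most lead-in dropouts would be withdrawals, already counted as severe.

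**The trial is exploratory.** Section 13.2 says so, and no decision rule uses p < 0.05. That lowers the stakes, not the need for a defined endpoint.

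**Conclusion.** The concern holds in a limited form. The no-assessment rule lacks a radiation-period limit, so under protocol-compliant conduct it catches almost nobody. A patient who stays on study, is unscored or stops being scored during radiation, and has no grade 3 or 4 in follow-up falls outside both rules. That patient counts as SOM-free and most naturally gets 0 days. A patient last scored at grade 3 or 4, with no later score and no death or withdrawal, has no defined duration.

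Each affected patient is worth 10 percentage points of incidence and, on the 24-day assumption, 2.4 days of mean duration. How many there will be is unknown and probably small. The p-values rest on assumed counts and show only that one patient can matter. The documents do not support reading this as every patient with missed radiation scores being credited with the best outcome, or as a bias known to favour RRx-001.

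**What to change.** In Section 13.2:

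1. Replace the no-assessment sentence with: *Patients with no OM assessment after the first IMRT fraction will be assumed to have severe scores.* Tying it to the first planned day of IMRT would not work, because the Day 15 pre-chemoradiation score would satisfy it.
2. Add: *A patient with no grade 3–4 observed whose scoring stops before the end of IMRT and does not resume is treated for SOM incidence as a withdrawal. A patient last scored at grade 3–4 with no later score is assumed to have SOM for the remainder of the observation period, as for a withdrawal.*
3. State the duration for patients imputed severe without an observed onset, for example from the first missed scheduled score to the end of the observation period, so that incidence and duration agree. That end needs a date: Section 6.1 describes evaluation for up to 6 weeks after radiation, while Sections 1.2 and 11.1 continue until grade 1 or less.
4. Apply the same rules to ulcerative OM at its own grade threshold.

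Do not reclassify as SOM a patient fully scored through IMRT below grade 3 who misses only later follow-up scores. These sentences leave as observed a patient whose scores lapse during radiation but resume below grade 3. If the sponsor wants to cover that case, a minimum number of radiation-period scores would do it.

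The cost is a few sentences and no new data. The downside is that a few unobserved patients count against their arm.
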